2. BACKGROUND INFORMATION

2.1. Investigational product

ADA recommends brushing teeth twice daily with either a manual or power soft bristle toothbrush. Although the manual toothbrush is accepted and used widely, the efficient brushing movement that a power toothbrush generates helps remove plaque with little effort. This directly benefits adult users (including those with limited dexterity) and helps them to achieve and maintain good oral health.

The present investigational product is a rechargeable power toothbrush. The toothbrush has two speed settings. The brush head portion is removable for routine replacement. The circular brush head moves in a rotation-oscillation fashion. In the bristle configuration of the investigational device, the eight inner tufts include end-rounded nylon filaments, and the surrounding tufts include longer tapered filaments. This configuration was designed to fit tooth contours, in which the center bristles forming a flat rectangular area that covers the tooth surface, while the longer tapered bristles are designed to increase subgingival and interproximal access.

Two independent in-vitro efficacy studies have been conducted. The Subgingival Access Efficacy (SAE) and Interproximal Access Efficacy (IAE) are evaluated in-vitro using artificial plaque covered substrate placed around simulated anterior and posterior teeth.[1] The toothbrush is loaded with a 250 gram weight and controlled to brush in horizontal and vertical motions. The IAE was averaged over the results of horizontal and vertical brushing while the SAE over results of horizontal brushing. The IAE and SAE of the power toothbrush were found to be superior to an ADA reference flat trim manual toothbrush with statistical significance ($p<0.001$). Table 1 summarizes the in-vitro results conducted for the power and manual toothbrushes used in the study. The finding indicates that the tapered filament feature and unique bristle design enhance subgingival and interproximal access efficacies compared to a flat trimmed manual toothbrush.

Table 1. The Interproximal Access Efficacy (IAE) and Subgingival Access Efficacy (SAE) of the investigational power toothbrush product and an ADA reference manual toothbrush. The IAE and SAE are the result of the in-vitro efficacy study.[1]

Toothbrush	IAE (mm)	SAE (mm)
Power	11.3	1.40
Manual	9.8	0.02
% difference*	14%	194%

*% difference is the difference in percentage with respect to the average of the two numbers.

CONFIDENTIAL

Moreover, the unique bristle design differentiates this device from other commercially available power toothbrushes with a similar rotation-oscillation movement. The in-vitro study results have shown the unique bristle design has superior access efficacy when compared to a commercially available rotation-oscillation power toothbrush. (Data on file)

The in-vitro access efficacy studies evaluate the effectiveness of the unique bristle design only in plaque removal in hard-to-reach areas. In-vitro studies are not able to test the effectiveness of the brushing movement the power brush generates, which helps the user to brush more easily. Moreover, in-vitro brushing on artificial plaque papers is not able to evaluate the effectiveness in treating and reducing gingivitis. Therefore, a clinical study is crucial to determine the clinical significance of the product in effectively treating and reducing gingivitis.

2.2. Known potential risks and benefits

The investigational device has no known potential risks. The literature published over the last 30 years has reported the rotation-oscillation power toothbrush to be safe compared to manual toothbrushes.[2] Moreover, a recent systematic review by Cochrane showed there was no apparent relationship between the use of a power toothbrush and soft tissue trauma.[2]

The benefits of the investigational device are as follows:

1. The unique bristle configuration is effective in removing plaque in the difficult-to-reach interproximal and subgingival areas, which should improve overall oral health if used regularly.
2. The Cochrane Collaboration, an independent healthcare research group, reported that clinical research shows that rotating-oscillating toothbrushes reduce plaque and gingivitis more than manual toothbrushes.[2]
3. The rotation-oscillation brushing movement helps facilitate more thorough brushing and makes brushing easier. This could benefit users with limited dexterity, such as elderly, people with disabilities.

This study will be conducted in compliance with the protocol, Standard Operating Procedures (SOPs), Good Clinical Practices (GCPs) Guidelines and applicable regulatory requirements. All study materials are to be reviewed by the Marquette University Institutional Review Board (IRB) prior to the study.

3. STUDY OBJECTIVES

The objective of this 12-week, parallel-arm, single-blinded, clinical study is to investigate efficacy and safety of a new power toothbrush in comparison with a standard ADA accepted manual brush.

3.1. Primary objective

Primary objective is to evaluate effectiveness of the product on gingivitis reduction compared to a flat trim manual toothbrush.

3.2. Secondary objectives

Secondary objectives are to evaluate the following:

- Effectiveness on plaque removal

CONFIDENTIAL

- Hard and soft tissue damage

4. STUDY DESIGN

4.1. Clinical Parameters

4.1.1 Oral Cavity Exam/Oral Safety Exam

4.1.2 Modified Gingival Index[3]

4.1.3 Lobene Modified Turesky Plaque Index[4,5]

4.1.4 Full mouth periodontal charting of pocket depths and Bleeding Index

4.2. Description of Clinical Parameters

4.2.1. Oral cavity examination

Oral cavity examination for safety assessments will include evaluation of the lips, tongue, hard and soft palate, gingiva, all mucobuccal fold areas, inner surface of the cheeks and sublingual areas, tooth surfaces and restoration surfaces. All areas will be assessed and reported as normal or abnormal with an explanation of any abnormality. In particular, the cervical root area will be carefully examined.

4.2.2. Lobene modification of the Loe and Silness Gingival Index

The Modified Gingival Index³ (MGI) will be measured on six sites – mesio-buccal, buccal, disto-buccal, mesio-lingual, lingual and disto-lingual - of all teeth using a 0-4 scale.

0 = Absence of inflammation. Normal gingiva.

1 = Mild inflammation: slight change in color, little change in texture of any portion of, but not the entire marginal or papillary gingival unit.

2 = Mild inflammation: criteria as above but involving the entire marginal or papillary unit.

3 = Moderate inflammation: glazing, redness, edema, and/or hypertrophy of the marginal or papillary gingival unit.

4 = Severe inflammation: marked redness, edema, and/or hypertrophy of the marginal or papillary gingival unit, spontaneous bleeding, congestion, or ulceration.

9 = Missing tooth or non-gradable tooth surface: a tooth surface will be considered non-gradable due to the presence of a crown, an extensive cervical restoration or a hypoplastic surface which could interfere with cleaning or cause plaque accumulation. Any surface graded as a 9 will not be included in the data analysis.

4.2.3. Lobene Modification of the Turesky Plaque Index

Dental plaque will be evaluated using the Lobene modification⁴ of the Turesky modification of the Quigley-Hein Plaque Index (PI)⁵. Disclosing solution will be used to identify the plaque (2 tone disclosing solution to be painted on the teeth with a microbrush then 10 ml's tap water used to, swish, then rinse again with water). Plaque will be scored on six surfaces of all natural teeth (3 buccal, 3 lingual) or nearest uncrowned tooth using a 0 scale. Subjects will abstain from brushing for at least 7 hours but no more than 12 hours prior to their evaluation appointment.

0 = No plaque/debris

1 = Separate flecks of plaque at gingival margin

2 = A thin continuous band of plaque (up to 1 mm) at the gingival margin

3 = A band of continuous plaque up to 1/3 of the crown of the tooth

4 = Plaque covering at least 1/3 but less than 2/3 of crown of tooth

5 = Plaque covering 2/3 or more of the crown of the tooth

9 = Missing tooth or non-gradable tooth surface: a tooth surface is considered non-gradable due to the presence of a crown, an extensive cervical restoration or a hypoplastic surface which could interfere with cleaning or cause plaque accumulation. Any surface graded as a 9 will not be included in the data analysis.

4.2.4. Probing Pocket Depth

Full-mouth Probing Pocket Depth (PPD) will be measured on the six locations of each tooth (mesial-buccal, buccal, distal-buccal, mesial-lingual, lingual, distal-lingual) using a periodontal probe.

4.2.5. Bleeding On Probing Index

The Bleeding on Probing index (BOP) will be recorded from the gingival sulci of all teeth after periodontal probing at all six locations per tooth - mesial-buccal, buccal, distal-buccal, mesial-lingual, lingual, distal-lingual. The presence of any bleeding within 30 seconds of gentle probing will be considered a positive response and given a score of 1. Sites which do not bleed on probing will be scored as 0.

0 = No bleeding

1 = Bleeding

4.3. Primary endpoint

The primary endpoint of this study is reduction of gingivitis (change from baseline) as measured by BOP and MGI at baseline, and again at 12-week visits.

4.4. Secondary endpoints

The following indices and parameters are secondary endpoints.

- Reduction of BOP and MGI at two-week, four-week visits from the baseline
- Reduction of PPD at 2-week, 4-week and 12-week visits from the baseline
- Reduction in plaque by measuring PI at 2-week, 4-week and 12-week visits as well as after a single use
- Safety of the product: clinical examiners inspect for any hard or soft tissue damage
- Patient reported outcomes from an exit survey and user diary

[figure not shown]
CONFIDENTIAL

4.5. Study procedure

The study to be conducted will be single-blinded, randomized controlled, parallel design. The study population will consist of Seventy-two (72) male and female subjects conforming to the following admission criteria. The subjects meeting the admission criteria with an anticipation of 40% dropout rate will be stratified into two groups balanced for MGI, BOP, PI, and gender using screening data. In this single-blind design, product assignment will be randomized after screening, and only the PI and the Study coordinator will have access to the randomization key.

One group will be assigned to a new power toothbrush while the control group will be assigned an ADA approved manual toothbrush. The study involves a 12-week home use of the respective toothbrushes. Both groups will refrain from the regular use of mouthwash and any interdental device, such as floss, floss picks, toothpicks, water flossing device or interdental brush, during the length of the study. Written instructions on brushing and professional brushing demonstration will be provided at the outset of the study and each participant from both test and control groups will also receive a 2-minute timer to help them monitor their brushing time. Before each visit, subjects are expected to have at least 7 hours, but no more than 12 hours of accumulated, non-brushed, undisturbed plaque/debris.

The study includes four or five visits – screening, baseline, 2-week follow-up, 4-week follow-up and 12-week follow-up. Schematic 1 summarizes the study procedure and visits and Table 2 details procedures in this study. The Screening and the baseline visit may happen on the same day.

Schematic 1. Study and visit procedures

CONFIDENTIAL

CONFIDENTIAL

Visit 2: Baseline
(continued)

A

Use brush per instruction

PI examination after
brushing

Single use
result

Schedule next visit

Pre visit

7 – 12 hours of plaque
accumulation

Visit 3: Follow-up visit
at 2 weeks

Oral examination for tissue abrasion and MGI
by calibrated examiners

Periodontal probing for BOP and PPD
by calibrated examiners

Oral examination for PI
By calibrated examiners

Schedule next visit

Pre visit

7 – 12 hours of plaque
accumulation

Visit 4: Follow-up visit
at 4 weeks

[figure not shown]
Oral examination for tissue abrasion and MGI
by calibrated examiners

Periodontal probing for BOP and PPD
by calibrated examiners

Oral examination for PI
by calibrated examiner

Schedule next visit

A

CONFIDENTIAL

Table 2. Procedure overview during visits

Procedure	Performed by	Visit				
		Screening	Baseline	2-week	4-week	12-week
Plaque accumulation	Subject	X	X	X	X	X
Patient information						
Informed consent form	Study coordinator/staff	X				
Patient demographics	Study coordinator/staff	X				
Medical/dental history	Study coordinator/staff	X				
Oral examination	Blinded examiners					
Oral cavity abrasion exam	Examiners 1 and 2	X	X	X	X	X
Gingival Index (MGI)	Examiners 1 and 2	X	X	X	X	X
Probing Pocket Depth	Examiners 1 and 2	X	X	X	X	X
Bleeding Index	Examiners 1 and 2	X	X	X	X	X
Plaque Index	Examiners 3 and 4	X	X*	X	X	X
Examiner calibration	All examiners	X				X
Others						
Inclusion/exclusion criteria	Study coordinator/staff	X	X			
Prophylaxis	Dental hygienist					X
Randomization	Unblinded staff/study coordinator		X			
Product introduction and instruction	Unblinded staff/study coordinator		X			
Brushing at clinic	Subject		X			
Scheduling future visit	Study coordinator/staff	X	X	X	X	
Collect used brushes	Unblinded staff/study coordinator					X
Exit survey	Subject					X

*Twice

CONFIDENTIAL

Visit 1: Screening and enrollment

Subjects will be asked to report to the clinic with at least 7 but no more than 12 hours of accumulated, non-brushed, undisturbed plaque/debris. Prior to screening, subjects will sign a consent form after having gone over the consent with a member of the study staff and having all questions answered. In this visit, subjects will be asked about dental and medical history related to the admission and exclusion criteria.

At the screening exam, subjects will receive an oral soft tissue exam with periodontal probing, modified Gingival Index on the Ramfjord teeth, and the amount of stain and calculus will be noted. Following these examinations, the subject's plaque will be disclosed with Trace 28 solution (4 drops under tongue) and they will swish for 10 seconds. Next, subjects will rinse with 10 ml. of tap water twice for 10 seconds each. Disclosed plaque will then be recorded on buccal and lingual surfaces of the Ramfjord teeth using the Lobene modification of the Turesky Plaque Index. If baseline happens on the same day then full mouth GI and BOP will be carried out prior to disclosing for full mouth plaque measurements. Subjects who meet the admission criteria will be allowed to enroll. If a subject fails the screening exam due to oral disease such as, but not limited to dental caries and periodontitis, the subject will be appropriately referred to the main Marquette University School of Dentistry (MUSoD) screening clinic to insure that they will be given an opportunity for full diagnosis and treatment at the school of dentistry or some other appropriate clinic.

Each clinical index will be scored by one of two or three calibrated examiners. The oral cavity/oral safety exam and all measures of inflammation, the MGI, PPD and BOP will be carried out by examiners #1 and 2 while disclosing and scoring of the PI will be scored by examiners #3 and 4. A fifth examiner who is dual calibrated will be used if needed. Each examiner will be calibrated to the indices used, and will demonstrate repeatability of measures initially at the screening/calibration phase as well as during the study.

Visit 2: Baseline

Subjects who have signed consent form and met all the inclusion criteria and none of the exclusion criteria will be entered into the baseline procedure (day 0). This visit may occur the same day as screening.

In this visit, subjects will first be evaluated for signs of soft or hard tissue trauma, and then full mouth Modified Gingival Index followed by full mouth probing of pocket depth and assessment of BOP. Teeth with calculus will be recorded. After these data are recorded each subject will be disclosed and full mouth Plaque scores assessed and recorded by a calibrated examiner. Any scorable teeth that have plaque buildup on any six tooth sites will be recorded. The subjects will then leave the examining area to the randomization and toothbrush distribution area where they will be provided their assigned brush out of site of the examiners. Group A will be given a power toothbrush, while Group B will be given a manual toothbrush. Both groups will also be given a two minute timer and the same fluoride toothpaste (Colgate Cavity Protection toothpaste) as well as the appropriate set of written instructions on tooth brushing. The subjects in the test group will follow the instructions provided by the manufacturer, while subjects in the control group will be given a standard written and both groups provided visual instructions on proper brushing. A study staff member will be available to answer any questions pertaining to the instructions and coach patients toward optimal brushing technique. Then the subjects will be required to use the brush assigned for two minutes before being sent back to the examiner to

CONFIDENTIAL

have a post-brushing plaque index recorded. These pre- and post 2-minute brushing data will be collected to assess single use effect differences between the toothbrush types. Subjects will be reappointed and instructed to bring their assigned brush to the subsequent exam sessions in a brown bag to avoid unmasking any of the examiners.

Visit 3: Two-week follow-up

The first follow-up will take place two weeks after the baseline visit. Subjects can schedule the visit for any time between two days before and after the two-week use period (12-16 day range). Clinical examinations will be given to the subjects in the same order as the baseline visit with the exception that no second plaque index will be recorded. All subjects must present with 7 to 12 hours of undisturbed plaque. The oral safety exam will include a thorough examination of the gingiva to look for any signs of gingival trauma, irritation or abrasion. Any subjects who show signs of gingival trauma that appears to be toothbrush related will be exited from the study. The recorded findings will be reported as Adverse Events. In addition, any site in the mouth that shows an increase in probing pocket depth of 2 mm or greater from the baseline measurement will have that particular site treated with subgingival scaling and root planing or whatever the PI deems appropriate therapy. If subjects meet any of the discontinuation criteria, they will be withdrawn from the study.

Visit 4: Four-week follow-up

This visit should take place four weeks after the baseline visit within three days before and after the four week mark (25-31 day range). Subjects will receive full mouth examinations in the same order as the previous visit. Additionally, inspection for signs of gingival trauma and increase in PPD greater than 2 mm from the baseline will be conducted and evaluated. The PI will determine if any subject meets the discontinuation criteria as well as appropriate therapy to treat.

Visit 5: 12-week follow-up

In this visit, subjects will return the products, including manual toothbrush, or brush head, brush handle, and charger. The procedure is similar to the four-week follow-up visit, in which full mouth clinical examination will be carried out as before on each of the subjects. The subjects' disclosed plaque will be evaluated as usual. The examined results will be recorded. Prophylaxis will be carried out as needed.

The used brushes/brush heads will be returned to sponsor at the end of the trial and examined for wear as an additional measure of compliance.

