7. STATISTICAL ANALYSIS

Each of the two research groups' patients will be assessed clinically at four time points (Baseline, 2 weeks, 4 weeks and 12 weeks). These measures will be compared against one another and over time using a between-within factors repeated measures ANOVA.

Further evaluation of interproximal and marginal scores will also be evaluated with a post hoc analysis.

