7.2. Demographics and other baseline characteristics

Subject demographics (e.g. age and sex), oral care habits (e.g. flossing and smoking) and baseline characteristics (e.g. MGI, BOP and PI) will be presented by treatment group and in total. Measurements of recorded teeth with calculus will not be included in statistical analysis.

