7.3. Significance level

Unless stated otherwise, significance level is 0.05. A p-value may be complemented by confidence interval.

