7.4. Method

Reductions in gingivitis – BOP, MGI and PPD – and plaque – PI from baseline scores after 2 weeks, 4 weeks and 12 weeks of use will be evaluated. For each subject, mean score of each index will be calculated as well as reductions from baseline at three time points. Additionally, numbers of abrasion sites found will be compared.

Assuming evaluated scores for the test and control groups are denoted U_{Test} and U_{Control} , respectively, the null hypothesis will be tested.

$$H_0: U_{\text{Test}} - U_{\text{Control}} = 0$$

$$H_1: U_{\text{Test}} - U_{\text{Control}} \neq 0$$

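### Allocation is balanced on screening MGI, BOP, plaque index and gender, but section 7 names no covariates; if these factors predict the outcome, precision is lost and the test is modestly conservative

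*Combined protocol and SAP*

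**What the plan says.** **Allocation.** Section 4.5 says that eligible subjects "will be stratified into two groups balanced for MGI, BOP, PI, and gender using screening data". It also says that assignment is randomized after screening. It gives no algorithm, strata or cut-points. At screening, gingivitis is scored as "modified Gingival Index on the Ramfjord teeth", and plaque is scored on the same subset of teeth. The endpoint indices are full mouth. Screening and baseline may fall on the same day.

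**Primary endpoint.** Section 4.3 defines it as "reduction of gingivitis (change from baseline) as measured by BOP and MGI at baseline, and again at 12-week visits".

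**Analysis.** Section 7 states: "These measures will be compared against one another and over time using a between-within factors repeated measures ANOVA". The visits are baseline and weeks 2, 4 and 12, so baseline is one level of the time factor. Section 7.4 adds that for each subject the "mean score of each index will be calculated as well as reductions from baseline at three time points", and sets a two-sided null hypothesis of no difference between arms. Section 7.3 reads: "Unless stated otherwise, significance level is 0.05". No part of section 7 names a covariate, stratum or gender term for a between-arm comparison.

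**Other use of the balancing factors.** Section 7.2 says only that "baseline characteristics (e.g. MGI, BOP and PI) will be presented by treatment group and in total", which is descriptive.

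**The concern.** Balancing the arms on a factor that predicts the outcome removes that factor's share of the chance difference between arms. A model without the factor still counts its share as error. The reported standard error is then larger than the true sampling variability, confidence intervals are too wide, and the test rejects less often than its nominal level.

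Subtracting baseline does not cure this. A change score fixes the baseline coefficient at 1, so the change usually stays correlated with baseline.

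What is at stake is precision in a small trial with no slack in its numbers. There is also a prespecification issue: with no covariates named, adding them after unblinding would look selective.

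**Working it through.** **1. The plan's own figures (section 7.1).** The inputs are 44 evaluable subjects, 40% dropout and 72 enrolled. 44 / (1 − 0.40) = 73.3, or 74 in equal arms; the plan enrols 72, which is close. In the other direction, 72 × 0.60 = 43.2, just under 44. No effect size, SD or correlation is given, so neither the 44 nor any loss of power can be checked from the documents.

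**2. Ceiling under perfect balance.** Let R² be the share of the variance of the change that the balancing factors explain. The unadjusted standard error is too large by 1/√(1 − R²), and the true level is 2 × [1 − Φ(1.96/√(1 − R²))]. Suppose that the factors act only through the outcome's own baseline, with equal variances and baseline-to-week-12 correlation r. Then R² = (1 − r)²/[2(1 − r)] = (1 − r)/2.

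| r (assumed) | R² | SE factor | True level |
|---|---|---|---|
| 0.3 | 0.35 | 1.24 | 1.5% |
| 0.5 | 0.25 | 1.15 | 2.4% |
| 0.7 | 0.15 | 1.08 | 3.4% |

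At R² = 0 the level is exactly 5%. Noisy screening scores, imperfect balancing and dropout all pull the real level back towards 5%.

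**3. Simulation under the null.** All settings use 72 subjects. The allocation methods, correlations and gender effects are assumptions, because the documents give none. The r values are 0.3–0.7. Entries are the true level of the unadjusted 12-week change-score test.

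| Setting | All 72 followed | 40% dropout |
|---|---|---|
| A: minimisation (0.9 preference), screening–baseline correlation 0.8, gender effect 0.4 SD; 4,000 trials per cell | 2.2–3.2% | 3.7–4.0% |
| B: minimisation on dichotomised factors (biased coin 0.8), correlation 0.9; 20,000 trials | 3.3–4.3% (4.5% at correlation 0.6, r = 0.5) | 4.0–4.5% |
| C: inputs of A with dichotomised factors; 6,000 trials | 3.0–3.8%; 3.5–4.2% with no gender effect | 3.4–5.2% (stratified blocks and minimisation) |
| D: minimisation; 3,000 trials | 3.1–4.7% | 3.9–4.6% |

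Monte Carlo error matters. With 3,000 trials and a 4% level, the standard error is √(0.04 × 0.96/3,000) = 0.36 points. In B it is about 0.15 points. Differences of a few tenths between settings should not be over-read.

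A control run with no balancing gave 4.9%, so the shortfall comes from balancing without adjustment. With all balancing factors and the baseline index as covariates, B gives 4.9–5.1%. With all balancing factors, A gives 4.7–5.0%, and full adjustment in D gives about 4.5–5.3%.

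**4. The ANOVA that section 7 names.** In B, across scenarios, the arm-by-visit interaction runs at 4.0–4.6% and the arm main effect at 1.2–3.6%. The main effect is hit hardest because it averages in the balanced baseline. Section 7 does not say which effect is the primary test.

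**5. Standard error against its true value.** In A, the mean model SE over the empirical SD, for r = 0.3, 0.5 and 0.7, is:
- All 72 followed: 0.279/0.244 = 1.14, 0.235/0.215 = 1.09, 0.182/0.169 = 1.08.
- About 44 completers: 0.359/0.338 = 1.06, 0.304/0.294 = 1.03, 0.234/0.224 = 1.04.

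**6. Standard error against the adjusted model, 40% dropout.** D gives about 4–20% larger. B gives ratios of 1.184, 1.103 and 1.034 for r = 0.3, 0.5 and 0.7. At r = 0.5, 1.103² = 1.217 and 44/1.217 = 36. The unadjusted interval from 44 completers is then about as wide as an adjusted one from 36.

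**7. Power illustration.** With an assumed difference of 0.8 SD, r = 0.5 and 40% dropout (3,000 trials), power is 0.74 for the change score, 0.83 with the outcome's baseline as covariate and 0.81 with all factors.

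**The case against.** The case for leaving the plan alone is that the effect is small, conservative and unproven. It depends on an allocation method and a prognostic strength that the documents do not state, and it vanishes if the factors do not predict the change. Several features weaken the balance: scores on a subset of teeth stand in for full-mouth values, and 40% of subjects may leave. At the planned dropout, the shortfall in level is about half a point to 1.3 points. All of this stands, and it limits how firmly the point can be put.

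A second argument is that the outcome's own baseline is the covariate that matters. This largely stands. With baseline alone as covariate and about 44 completers, the level in setting A is already 4.6–5.0%, and in the power illustration the further factors gain nothing. Adding the balancing factors is justified mainly by matching the analysis to the allocation: with all 72 followed and a gender effect, baseline alone leaves A at 3.8–4.3%.

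Three stronger readings are tempting, and the documents support none of them:
- **That the test is known to run well below 5%, at 2–3%.** Those figures need near-complete follow-up, close balancing and an assumed gender effect.
- **That the balancing variables are wholly absent from the analysis.** The outcome's own baseline enters by subtraction and as a level of time. Gender, the screening scores and the other indices are what is missing.
- **That the primary result would be invalid.** This source adds no false positives. The lack of a multiplicity rule for BOP and MGI, and of a named sphericity correction, are separate matters that can push error the other way.

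**Conclusion.** The mismatch between allocation and analysis is in the text. Its direction is clear, provided that the balancing factors predict the outcome. Its size is an estimate, not something the documents give.

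- **Test level:** roughly 3.7–4.6% in place of 5% at 40% dropout (settings A, B and D: minimisation, screening–baseline correlation around 0.8–0.9 where stated, r from 0.3 to 0.7). If all 72 are followed, the spread over all settings is roughly 2–4.7%.
- **Precision:** at 40% dropout, an unadjusted standard error about 4–20% larger than the adjusted one (3–18% in setting B). This is the larger loss, and most of it comes from entering baseline by subtraction and not as a covariate.

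Confidence is high on the omission and the direction, and moderate on the size. The plan should be changed because the remedy is cheap. The trial is sound without it, only less precise.

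**What to change.** In section 7, before unblinding:

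1. State that the primary between-arm comparison of 12-week MGI and BOP, and the comparisons of the continuous secondary indices (plaque index and pocket depth), use ANCOVA or a mixed model. The prespecified covariates are the full-mouth baseline value of the outcome, gender, and the screening MGI, BOP and plaque index used for allocation, with the indices kept continuous.
2. Take the primary p-value and 95% confidence interval from that model, and show the unadjusted result as supportive.
3. In section 4.5, state the balancing method (algorithm, and any strata or cut-points), so that the model can match it.
4. Do not require the full covariate set for abrasion-site counts or survey outcomes, where data may be sparse.

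**Cost.** Wording only: Table 2 shows the factors collected at screening, before assignment. Five covariates take five degrees of freedom; with 44 completers, 44 − 2 − 5 = 37 remain for a single-visit ANCOVA. Screening and baseline scores of the same index will be partly collinear. That makes their own coefficients unstable, but it is not a problem for the arm comparison.
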